eFramingham Heart Study Randomized Controlled Trial #2

NCT04752657

[name] ScM

[contact]

Email: [contact]

October 2020

Statistical Analysis Plan- pages 4-5

eFHS Offspring/Omni Protocol

The objective is to test the effect of administering half of survey modules every 2 weeks versus all survey modules every 4 weeks on improving participants' response rates.

Methods

We prepared the protocol for this randomized factorial trial in compliance with the [SPIRIT checklist](#) and plan to register the trial on clinicaltrials.gov.

Study setting and Eligibility criteria

Our randomized controlled trial will include participants of the electronic Framingham Heart Study (eFHS). Participants in eFHS are invited to enroll from the FHS Offspring and Omni Group 1 Cohorts during the in-person examination 10/5 at the FHS Research Center in Framingham, MA, USA or remotely from home after the in-person examination. In order to be eligible in the eFHS, individuals have to meet the additional following criteria: English-speaking individual who owns an iPhone with compatible iOS (version 10.0 or higher) or Android (version 5.0 or higher); residence in the United States; provision of permissions for notifications and data sharing with the Research Center; provision of signed and dated informed consent (within the eFHS mobile app). Enrollment in the randomized controlled trial will start once approved by IRB.

Surveys and Interventions

All eFHS participants have the eFHS myDataHelps mobile app (developed by FHS investigators with CareEvolution our industry partner) installed on their smartphone. The eFHS app allows communication with participants through notifications and data collection. Participants are asked to answer health surveys administered through the app.

Survey assessments will include 6 modules: cognition, pain, mood, physical function and performance, physical activity, and events (table 1). The interventions are defined by the patterns of administration of survey modules to the experimental and control groups as described in Table 2. The administration of the cognition, pain, mood, and psychosocial

eFHS Offspring/Omni Protocol

modules follow the same pattern for both groups. However, the administration of the physical function, physical activity, and events modules is shifted for the experimental group as compared to the control group.

The cognition and gait tasks are currently not available on android phones. Thus, we will not administer these modules to participants who have an android phone instead of an iphone and these participants will contribute data only to the other survey modules.

Table 1: survey modules

Cognition	
Trails	Task
Stroop	Task
Tapping	Task
Cognitive function	4-items
Cognitive abilities	4-items
Pain	
Pain Q (past 7 days)	5 items
Body Map (past 3 months)	
Mood	
Depression (past 7 days)	4 items
Anxiety (past 7 days)	4 items
Loneliness (no timeframe)	3 items
Psychosocial parameters (loneliness, social support, resilience)	3-items, 8-items, 11-items, 6-items
Physical function/performance	
Gait	Task
Mobility no timeframe	4 items
Sleep (past 7 days)	4 items
Fatigue (past 7 days)	4 items
Mobility outside home (past 4 weeks)	5 items (with more if yes)
Physical activity	
RAPA (no timeframe)	9 items
Events	
Falls/hospitalzn (past month)	2 items (with more if yes)

eFHS Offspring/Omni Protocol

Table 2: pattern of administration of survey modules in the experimental and control groups

Week	0	2	4	6	8	10	12	14	16	18	20	22	24	26
Cognition	✓				✓				✓				✓	
Pain	✓		✓		✓		✓		✓		✓		✓	
Body map	✓						✓						✓	
Mood	✓					✓			✓				✓	
Psychosocial				✓			✓				✓			
Physical function	✓	✓				✓	✓		✓	✓			✓	✓
Physical activity	✓	✓					✓	✓					✓	✓
Events	✓	✓	✓	✓	✓	✓	✓	✓	✓	✓	✓	✓	✓	✓
# modules														
Exp. group	7	3		5		5		5		3		7		
Control group	4	3	2	1	3	2	3	2	3	2	2	1	4	3
	■	Administration to both groups												
	■	Administration to control group												
	■	Administration to experimental group												

Participants will be able to complete a survey module from its administration until the next wave.

This time varies across survey modules given the frequency and timing of administration. For example, participants will be able to complete the first pain module between week 0 and week 4 post-randomization and they will be able to complete the last pain module between week 24 and week 28. For the physical function module, the first survey can be completed between week 0 and 8 in the control group and between week 2 and 10 for the experimental group; while the last survey can be completed between week 24 and 32 in the control group and between week 26 and 34 in the experimental group.

All participants will periodically receive notifications through the eFHS app to remind them to answer the surveys on the eFHS app. Based on our previous work, we will send personalized notifications, that include the name of participants and account for the number of surveys already completed, to improve response rate to surveys.¹ One week after randomization, we also will contact all participants by telephone to inquire about any technical issue with the app.

eFHS Offspring/Omni Protocol

Duration of trial

We will conduct the trial over 32 weeks.

Outcomes

We define 4 survey periods. Period 1 encompasses all survey modules administered from baseline up to week 8 (19 surveys/tasks per participant); period 2 from week 8 up to week 16 (18 surveys/tasks per participant); period 3 from week 16 up to week 24; period 4 from week 24 (16 surveys/tasks per participant).

The primary outcome is the proportion of surveys/task returned per participant (partially or fully completed). The secondary outcome is the proportion of questions/task completed per participant. For both the primary and secondary outcomes, we will compare the mean proportions assessed longitudinally across the 4 periods between the experimental and control groups.

Random allocation

We will randomly allocate each participant to one of the 2 groups. A statistician will generate randomization lists with the use of randomly permuted blocks of varying sizes, with stratification according to participant's age (≤ 75 years vs. > 75 years) and type of phone (android vs. iphone). Randomization will be implemented centrally through the app.

eFHS researchers and statistician will be masked to the group assignment. As part of eFHS, support staff help participants complete their remote monitoring and data transmission. The support staff uses standardized scripts to interact with participants over the phone to address technical questions.

Sample size

We calculated the sample size for the comparison of the mean proportion of surveys returned between the two groups across time. We assumed consistent difference over time and that the

eFHS Offspring/Omni Protocol

distribution of the sample proportions are approximately normally distributed. We account for 4 time periods. We very conservatively assumed a correlation of the repeated measures of 0.6 and a standard deviation on the proportion of survey returned of 20%. A sample size of 300 participants per group guarantees 95% power to detect a mean difference of 5% between groups, for example between a mean of 50% of surveys returned per participants in the control group vs. a mean of 55% of surveys returned per participants in the experimental group.

Statistical methods

We will use a mixed-effects regression model to compare the mean proportions between groups across time. Analyses will be in intention-to-treat. We will fit random-intercept models as well random-intercept and random-trend models.

We will perform the following a priori subgroup analyses. We will assess and compare the primary and secondary outcomes in subgroups defined according to age (> vs. \leq 75 years), sex (female vs. male), type of phone (iphone vs. android), cognitive status (impaired or not) and whether participants have an apple watch or not. The cognition and gait tasks are currently not available on android phones.

eFHS Offspring/Omni Protocol

References

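### The stated 32-week duration conflicts with the experimental arm's last physical-function window, which runs to week 34

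*Combined protocol and SAP*

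**What the plan says.** The Duration of trial section is a single sentence: "We will conduct the trial over 32 weeks".

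The text after Table 2, under Surveys and Interventions, sets the general rule that a module stays open until its next wave is issued. It then works through two examples. The pain example counts weeks from randomization. For physical function, "the first survey can be completed between week 0 and 8 in the control group and between week 2 and 10 for the experimental group"; at the end of the schedule, "the last survey can be completed between week 24 and 32 in the control group and between week 26 and 34 in the experimental group".

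The introduction to the interventions says that physical function, physical activity and events are the modules shifted in the experimental group.

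The Outcomes section defines four periods by when modules are administered. The last one begins at week 24 and has no stated end. The primary outcome is each participant's proportion of surveys or tasks sent back, complete or partial, compared between groups across the four periods.

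**The concern.** The duration ends exactly when the control window closes and two weeks before the experimental window does. Someone programming the data cut therefore has two statements that cannot both be applied, and no rule for choosing between them.

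The choice matters because the endpoint is whether surveys come back, so the time allowed for return is part of how the outcome is measured. A cut at week 32 would shorten that time in one arm only. The cause would be the two-week shift that defines the intervention, so neither randomization nor an intention-to-treat analysis would correct it. The direction would be against the experimental arm: a real benefit could be understated, but the shorter window would not create a false one.

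**Working it through.** **Inputs**
- Duration: 32 weeks (Duration of trial).
- Physical-function windows: first wave 0–8 control and 2–10 experimental; last wave 24–32 control and 26–34 experimental (text after Table 2).
- Last pain window: 24–28 (same text).
- Spacing of the other modules: read from the ticks in Table 2. The shading that separates the arms is lost in the copy read here, so arm-specific weeks for physical activity and events are inferred from the stated shift.

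**Step 1. Reproduce the stated figure.** Last administration plus window length, control arm: 24 + 8 = 32. The plan's figure is recovered from the control arm alone. Four periods of 8 weeks also give 4 × 8 = 32.

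**Step 2. Same formula, experimental arm.** 26 + 8 = 34. The overrun is 34 − 32 = 2 weeks.

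**Step 3. Is the week-34 figure a slip?** Window lengths are 8 − 0 = 8, 10 − 2 = 8, 32 − 24 = 8 and 34 − 26 = 8. The shift between arms is 2 weeks at both ends of the schedule. The windows agree with each other and with the description of the intervention. The duration is the figure that does not fit.

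**Step 4. What a cut at week 32 would do to physical function.**
- Control: 32 − 24 = 8 of 8 weeks (100%).
- Experimental: 32 − 26 = 6 of 8 weeks (75%).

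**Step 5. Other final-wave modules under the general window rule.**

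| Module | Last wave + spacing | Closes at week | Weeks available by week 32 |
|---|---|---|---|
| Pain (both arms) | 24 + 4 | 28 | 4 of 4 |
| Cognition (both arms) | 24 + 8 | 32 | 8 of 8 |
| Events, control | 24 + 4 | 28 | 4 of 4 |
| Events, experimental | 26 + 4 | 30 | 4 of 4 |
| Body map (both arms) | 24 + 12 | 36 | 8 of 12 |
| Physical activity, control | 24 + 12 | 36 | 8 of 12 |
| Physical activity, experimental | 26 + 12 | 38 | 6 of 12 |

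So physical activity would apparently also have 8 weeks in control against 6 in the experimental arm. Body map would be cut short equally in both. Covering the windows stated in the text needs at least 34 weeks from randomization. Applying the general rule to every module in the table needs up to 38.

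**Step 6. Size of the bias.** This needs the share of experimental-arm returns that would arrive after week 32. The documents give nothing on response timing, so no figure follows.

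**The case against.** The strongest reply is that nothing would go wrong in practice. No section makes week 32 a data cut-off. The specific rules (modules open until the next wave, an explicit 26–34 window, periods set by administration) all point to counting returns up to week 34. A one-line duration is weak ground for overriding them. This stands, and it limits the point to an inconsistency that would do harm only if the duration were applied literally.

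A second reply is that 32 weeks may simply denote four nominal 8-week periods. That is possible, but the plan does not say so, and the experimental window would still be open until week 34. Nor do the documents show that the figure arose by overlooking the shift. If 32 weeks meant total calendar time, staggered enrolment would widen the mismatch.

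A reader might try to size the effect from the item count. Physical function has five components in Table 1 and the plan gives 16 surveys or tasks for Period 4, so 5/16 = 31% looks exposed. The documents do not support that as a firm figure:
- The count needs a reconstructed rule, with loneliness counted only under psychosocial and psychosocial counted as one survey. It gives Period 4 as 5 + 1 + 1 + 2 + 0 + 5 + 1 + 1 = 16 (cognition, pain, body map, mood, psychosocial, physical function, physical activity, events). The same rule gives Period 2 as 5 + 2 + 1 + 2 + 1 + 5 + 1 + 2 = 19, where the plan states 18.
- Android users receive no gait or cognition tasks. Their share would be 4/10 if the whole cognition module is dropped, or 4/12 if only its three tasks are.
- If physical activity is affected too, the iPhone share becomes 6/16.

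Any conversion of these shares into percentage points would also rest wholly on an assumed proportion of late returns.

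**Conclusion.** The plan contradicts itself by two weeks: a 32-week trial cannot contain a completion window that closes at week 34. Both figures stand in running text, and no other section reconciles them.

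The consequence is conditional. If 32 weeks governs data collection, the last physical-function survey gets 6 weeks in the experimental arm against 8 in control, and the primary outcome is ascertained differently in the two arms, to the disadvantage of the experimental one. Physical activity would apparently follow the same pattern, subject to the reading of Table 2. If the stated windows govern, there is no bias and only the duration needs correcting.

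A reader might infer that the primary comparison is biased as planned, or that Period 4 is undefined because it has no end week. Neither follows: no cut-off at week 32 is stated, and membership of Period 4 depends on when a module is administered.

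Severity is minor. It is an inconsistency in a figure that someone will have to act on, with an arm-specific effect if it is acted on literally.

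**What to change.** Reconcile the Duration of trial section with the final completion windows by stating one data cut-off rule that gives every final-wave module the same window length in both arms, counted from its administration. Then restate the duration to match:
- **Windows stated in the text:** at least 34 weeks from randomization.
- **General rule kept for the 12-weekly modules (body map and physical activity, as read from Table 2):** up to about 38 weeks.
- **Alternative:** set a shorter final window, common to both arms, and derive the duration from that.

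The edit is one figure and one sentence. The cost is a data cut later by about 34 − 32 = 2 to 38 − 32 = 6 weeks, depending on the rule chosen; a shorter common window would reduce this. The rule should be settled before the data cut.

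### Randomisation is stratified by age and phone type, but the mixed model names neither as a covariate; if they predict survey return, the intervals are wider than they need to be.

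*Combined protocol and SAP*

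**What the plan says.** Under Random allocation, the lists use "randomly permuted blocks of varying sizes, with stratification according to participant's age" (75 years or under against over 75) and also type of phone (Android against iPhone).

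Under Statistical methods, the comparison is described in one sentence: "We will use a mixed-effects regression model to compare the mean proportions between groups across time". The analysis is by intention to treat, and the random effects are given as "We will fit random-intercept models as well random-intercept and random-trend models". No baseline covariate is named. Age and phone type come back only in the subgroup paragraph: "We will assess and compare the primary and secondary outcomes in subgroups defined according to age", with phone type further down the same list.

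Under Sample size, the plan states: "A sample size of 300 participants per group guarantees 95% power to detect a mean difference of 5% between groups". It assumes a standard deviation of 20 points, a correlation of 0.6 between repeated measures and four periods. That section gives no significance level.

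**The concern.** Permuted blocks within strata make the arms nearly equal in their mix of age and phone type. Differences in return between strata then contribute almost nothing to the real sampling variation of the group difference. A model without the strata does not know this. It counts stratum differences as ordinary between-participant variation and reports a standard error that is too large.

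The participant random intercept does not cure the problem. It absorbs the stratum differences into the between-participant variance, which is the component that drives the standard error of the group effect. The subgroup analyses do not cure it either, because they leave the overall estimate and its standard error unchanged.

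What is at stake is precision. Confidence intervals would cover more than 95% of the time, the test would reject less often than its nominal level, and part of the benefit of stratifying would be lost.

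**Working it through.** **Inputs from the Sample size section:** 300 per group, standard deviation 0.20, correlation 0.6, four periods, difference 0.05.

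**Assumed:** two-sided significance level of 0.05; and R², the share of the variance of participants' four-period means explained by the two factors. The documents give no value for R², so a range is shown.

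**Step 1: the plan's own figure.**
- Variance of a participant's four-period mean: 0.04 × (1 + 3 × 0.6)/4 = 0.028, a standard deviation of 0.1673.
- Standard error of the difference: √(2 × 0.028/300) = 0.01366, so the 95% half-width is 1.96 × 0.01366 = 2.68 points.
- Power at 5 points: Φ(0.05/0.01366 − 1.96) = 95.5%.

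This agrees with the stated 95%. A one-sided 0.05 test would give 97.8%, and ignoring the repeated measures would give 86.5%, so the two-sided repeated-measures calculation is the one that fits.

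**Step 2: effect of leaving out the strata.** Under stratified allocation the true standard error is about 0.01366 × √(1 − R²), but the unadjusted model reports 0.01366. Hence:
- excess interval width = 1/√(1 − R²) − 1
- true type I error = 2 × [1 − Φ(1.96/√(1 − R²))]
- unadjusted power = Φ((0.05 − 1.96 × 0.01366)/true SE)
- adjusted power = Φ(0.05/true SE − 1.96)

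| R² (assumed) | Half-width, unadjusted / adjusted (points) | Excess width | Type I error, unadjusted | Power, unadjusted / adjusted | Gain (points) |
|---|---|---|---|---|---|
| 0% | 2.68 / 2.68 | 0% | 5.0% | 95.54% / 95.54% | 0 |
| 5% | 2.68 / 2.61 | 2.6% | 4.4% | 95.94% / 96.37% | 0.4 |
| 10% | 2.68 / 2.54 | 5.4% | 3.9% | 96.34% / 97.11% | 0.8 |
| 20% | 2.68 / 2.40 | 11.8% | 2.8% | 97.13% / 98.35% | 1.2 |

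Unadjusted power rises with R² because the total standard deviation is held at the plan's 20 points while the true sampling error shrinks.

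**Step 3: what R² might mean in practice (illustration only).** Assume 20% Android users, half of participants over 75, and the two factors independent. Then R² = [0.16 × (phone gap)² + 0.25 × (age gap)²]/0.028.
- 5-point gaps on both: 0.001025/0.028 = 3.7%, interval 1.9% too wide.
- 10-point gaps on both: 0.0041/0.028 = 14.6%, interval 8.2% too wide.

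**Step 4: simulation check.** Settings: 600 participants, permuted blocks of 2, 4 or 6 within the four strata, 6,000 trials per setting, analysis of participants' four-period means. Block sizes and the strata shares (20% Android, 40% in one age group) are assumed. The Monte Carlo error is √(0.05 × 0.95/6,000), about 0.3 points.

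| R² | Type I error, unadjusted | Type I error, with the two fixed effects |
|---|---|---|
| 0% | 5.4% | 5.4% |
| 5% | 4.2% | 4.9% |
| 10% | 3.9% | 4.9% |
| 20% | 3.0% | 5.3% |

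At R² of 20% with no true difference, the unadjusted model reported a standard error of 1.366 points while the estimates actually varied with a standard deviation of 1.231. The adjusted model reported 1.222.

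**The case against.** The strongest reply is that this rests on silence. The Statistical methods are a short summary that lists no covariates at all, so an analyst who adjusted for the strata would not breach the plan. That is true, but the same wording equally permits the unadjusted model. The consequence described here applies if the model is fitted as written.

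Second, nothing in the documents shows that age or phone type predicts return. The Surveys and Interventions section says that Android users are not given the cognition and gait tasks. This changes which items make up their proportion, but does not show that they return a higher or lower share. This stands: every non-zero figure above depends on an assumed R².

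Third, the harm is small. With 5-point gaps on both factors, each as large as the trial's target difference, the half-width falls only from 2.68 to about 2.63 points on adjustment (2.68 × √(1 − 0.037)). The 20% row needs more than the illustrative 10-point gaps produce. This also stands, and limits the point to an inexpensive improvement.

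Fourth, the simulation used four-period means. That matches a random-intercept model with a constant group difference. The model with a random trend, and any group-by-time comparison, were not simulated. The direction should carry over, but the exact percentages are not shown for them.

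**Conclusion.** The concern holds. Age and phone type are stratification factors, and the stated model includes neither. To the extent that they predict return, the unadjusted analysis is conservative: for R² between 0% and 20%, intervals are 0% to 11.8% too wide and true type I error is between 5.0% and 2.8%.

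The estimate stays unbiased, false positives are not inflated, and power stays at 95.5% or above on the plan's own inputs, so the design is not threatened. The direction follows from the stratified design. The size rests on the assumed R² and the assumed two-sided 0.05 level, and is nil if the factors do not predict return. This is worth considering as a low-cost gain in precision.

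**What to change.** Add one sentence to the Statistical methods: the primary and secondary mixed models include fixed effects for the randomisation strata, age (75 years or under against over 75) and phone type (Android against iPhone).

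Both variables are known for every participant at randomisation, so no data are lost. The cost is two degrees of freedom out of about 600 participants. The sentence also settles in advance whether the reported analysis is adjusted.

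### Does planning two mixed models without naming a primary one leave the group comparison, or its 95% power, undefined?

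*Combined protocol and SAP*

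**What the plan says.** The Statistical methods section describes the primary analysis briefly. The aim is "We will use a mixed-effects regression model to compare the mean proportions between groups across time", the analysis is by intention to treat, and on model form the text says only "We will fit random-intercept models as well random-intercept and random-trend models". It names no primary model, time coding, group-by-time term, tested coefficient or significance level.

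Two other sections describe the same comparison. Outcomes says of the primary and secondary outcomes that "we will compare the mean proportions assessed longitudinally across the 4 periods between the experimental and control groups". Sample size powers a difference in mean proportion with four periods, an SD of 20% and a correlation of 0.6. It adds "We assumed consistent difference over time" and concludes "A sample size of 300 participants per group guarantees 95% power to detect a mean difference of 5% between groups". Its example is "a mean of 50% of surveys returned per participants in the control group vs. a mean of 55% of surveys returned per participants", where the second figure belongs to the experimental arm.

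**The concern.** Two models with no ranking invite a choice after the data are seen. The phrase about comparing groups across time could be taken to mean the average of the four period differences or a difference in slope, and the mention of a random trend makes the second reading easier to reach. If a linear time term and a group-by-time term were added with time starting at zero, the group coefficient would become the first-period difference and no longer the average.

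These tests differ in power. The sample size calculation covers a constant 5-point difference, and a slope test has no power against that. Choosing the most favourable of several tests would also raise the false-positive rate. On this view the 95% would belong to a test that might not be the one reported.

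**Working it through.** **Inputs.** From Sample size: 300 per group, SD 0.20 within a period, correlation 0.6, four periods, constant difference 0.05. Assumed: a two-sided 5% level, since none is stated.

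**1. The plan's own figure.** A common correlation of 0.6 splits the variance 0.04 into a shared part of 0.6 × 0.04 = 0.024 and a residual part of 0.016. This is the covariance that a random-intercept model implies. For the four-period average:

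- SE = √[(2/300)(0.024 + 0.016/4)] = √[(2/300)(0.028)] = 0.01366
- z = 0.05/0.01366 = 3.66
- power = Φ(3.66 − 1.96) = 95.5%

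The size needed for 95% power is 292 per group, so 300 fits. Other levels miss the stated figure: one-sided 5% gives 97.8%, two-sided 2.5% gives 92.2% and two-sided 1% gives 86.1%. A single period at two-sided 5% gives 86.5%. Of the options tried, only the four-period average at two-sided 5% matches, so the power statement itself points to the contrast and the level.

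**2. Contrasts that the plan does not propose,** under the same inputs:

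| Test | Calculation | Power |
|---|---|---|
| Period-1 coefficient with group-by-linear-time term | weights (0.7, 0.4, 0.1, −0.2), sum of squares 0.70; SE = √[(2/300)(0.024 + 0.70 × 0.016)] = 0.01532 | 90.4% |
| Joint test of four period differences | 4 df, noncentrality 3.66² = 13.39 | 84.9% |
| Group-by-trend | weights sum to zero, so noncentrality is 0 | 5.0% |

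The average and trend tests are independent under this covariance, so reporting either gives 1 − 0.95² = 9.75%, about 9.8%. Adding the period-1 coefficient gives 11.2% by simulation.

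**3. The choice actually written: random-effects structure, one group effect.** Take intercept variance 0.024, residual variance 0.016, time 0 to 3, and add a random slope. Its SD and its correlation with the intercept are assumed, since the documents give neither. The random-trend model weights the periods in proportion to S⁻¹1, where S is the implied covariance matrix. In balanced data the random-intercept model weights them equally. The correlation of the two estimators is the ratio of their SEs (weighted over equal). The chance that at least one is significant under no effect follows from the bivariate normal.

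| Slope SD, correlation | Period weights | Correlation of estimators | False-positive rate, either model |
|---|---|---|---|
| 0.03, −0.5 | 0.18, 0.23, 0.27, 0.32 | 0.995 | 5.5% |
| 0.03, −0.3 | 0.25 each | 1.000 | 5.0% |
| 0.05, 0 | 0.45, 0.32, 0.18, 0.05 | 0.963 | 6.3% |
| 0.05, +0.3 | 0.57, 0.36, 0.14, −0.07 | 0.917 | 6.9% |

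The weights sum to 1 in each row, so a constant 5-point difference is estimated as 5 points by both models.

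**4. Power under the random-trend model.** In the first row above, the random-trend group effect has 98.2% power and the equal-weight average 98.1%. With the average period variance held at the plan's 0.20² and slope SDs of 2 to 6 points, the random-trend group effect has 95.8% to 99.3%. Choosing that model therefore does not forfeit the stated power in these settings.

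**The case for a change.** The strongest reply is that the constant difference is a sample size assumption and not an analysis rule. If the true difference grew as 2, 4, 6 and 8 points, the equal-weight average would be 5.0, while the random-trend group effect would target 5.5, 5.0, 3.7 or 2.9 in the four slope settings above. A first-period coefficient would target 2.0. The two planned models would then not always estimate the same quantity, and two sentences in the SAP would settle which one counts.

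Part of this stands. No primary model is named, and the averaged difference is not written as a model term with a level. But the divergence needs a growing effect that the plan does not assume. The widest gaps (3.7 and 2.9) also need period-4 SDs of about 25% and 28%, against the planned 20%, because slope variance has been added on top of the plan's total.

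Fixing equal weights would not be a clear gain either. In those two settings the equal-weight average has 91.6% and 86.0% power for a constant 5 points, below the random-trend group effect at 93.4% and 91.2%. The first-period and slope tests remain outside the plan: trend appears there only as a random effect, never as the parameter to be compared.

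**Conclusion.** The concern does not call for a change. The omission is real, but three sections describe one comparison, a difference in mean proportions over the four periods. The stated 95% power belongs to that comparison and reproduces at 95.5%. Followed as written, the plan gives a sound test under its own constant-difference assumption, and both models target the same 5 points.

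The written ambiguity costs a false-positive rate of about 5.0% to 6.9% if either model's group effect could be reported. The power figure rests on an assumed two-sided 5% level, and the error range on slope variances that the documents do not give and on balanced data. The figures of 5% power and of 9.8% and 11.2% false positives describe tests that the plan does not propose. A formal statement would mostly write down the contrast already described, without a better method or a different sample size.
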